4.7.2 Secondary Efficacy Analyses

The secondary efficacy analyses will be based on the mITT set on the following endpoints:

- Change from Baseline to Week 8 in Partial Mayo Score
- Change from Baseline to Week 8 in Histologic Assessment of Endoscopic Biopsy
- Change from Baseline to Week 8 in UCEIS Score
- Change from Baseline to Week 8 in SIBDQ

For each secondary efficacy endpoint described above, descriptive statistics will be presented by treatment and cohort group including mean, SD, median, max, and min. Similar to the primary efficacy analysis, mixed model repeated measures (MMRM) analyses will be performed for various secondary efficacy endpoints as noted above.

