## 8.3 Efficacy Assessments

- Total Mayo Score (Stool frequency, rectal bleeding, endoscopic findings [flexible proctosigmoidoscopy/colonoscopy], physician's global assessment): Screening and W8
- Partial Mayo Score: Baseline, W4, W8, W12, and W16
- Histologic Assessment of Endoscopic Biopsy: Screening and W8
- UCEIS score: Screening and W8
- SIBDQ: Baseline, W4, W8, W12, and W16
- Serum CRP: Baseline, W4, W8, W12, and W16
- Fecal calprotectin: Baseline, W4, W8, W12, and W16
- Fecal lactoferrin: Baseline, W4, W8, W12, and W16

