### 8.3.4 Quality of Life Questionnaire: Short Inflammatory Bowel Disease Questionnaire (SIBDQ)

The SIBDQ is a health-related quality of life (HRQoL) tool measuring physical, social, and emotional status. Scores range between 10 and 70, reflecting poor to good HRQoL. The SIBDQ has been predominantly used in trials for Crohn's disease, and further validation of the SIBDQ is desirable in UC patients. A sample of the SIBDQ is provided in [Appendix 3](#).

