4.7.1 Primary Efficacy Analysis

Descriptive statistics will be presented including mean, standard deviation (SD), median, max, and min by treatment and cohort group for the change from baseline to Week 8 in Total Mayo score. Also, to better assess the differences between each dose and the placebo for the change from baseline to Week 8 in Total Mayo score, a mixed model repeated measures (MMRM) analysis will be performed. The MMRM model will include treatment (whether 1st dose, 2nd dose, or 3rd dose vs. Placebo) and the baseline score as fixed effects, and center as a random effect. Restricted Maximum Likelihood (REML) with an unstructured variance-covariance matrix will be used for estimation in the MMRM analysis. If the fit of the model with the unstructured covariance structure does not converge, the following covariance structures will be tried in order until convergence is reached: Toeplitz with heterogeneity, autoregressive with heterogeneity, Toeplitz, and autoregressive. Each dose will be compared with placebo—model-based point estimates for the treatment effects and 95% confidence intervals (CIs) will be calculated.

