Note: Least Squares means, p-values were from MMRM model with treatment and baseline score as fixed effects, and center as random effect. Restricted Maximum Likelihood (REML) with an unstructured variance-covariance matrix is used for estimation in the MMRM analysis.

Table 14.2.2.1.1
 Summary of Change of Partial Mayo Score from Baseline to Week 8
 mITT Analysis set

Study Visit	Placebo (N=XX)	BBT-401-1S (N=XX)
Baseline		
n (missing)	XX (XX)	XX (XX)
Mean (SD)	XX.X (XX.XX)	XX.X (XX.XX)
Median	XX.X	XX.X
Min, Max	XX, XX	XX, XX
Week 8		
n (missing)	XX (XX)	XX (XX)
Mean (SD)	XX.X (XX.XX)	XX.X (XX.XX)
Median	XX.X	XX.X
Min, Max	XX, XX	XX, XX
Change from Baseline to Week 8		
n (missing)	XX (XX)	XX (XX)
Mean (SD)	XX.X (XX.XX)	XX.X (XX.XX)
Median	XX.X	XX.X
Min, Max	XX, XX	XX, XX
LS Mean (SE)	XX.X (XX.XX)	XX.X (XX.XX)
P-Value, Active vs Placebo		0.XXX
LS Mean Difference (SE)		XX.X (XX.XX)
95% CI for Differences		(XX.X, XX.X)

Note: Least Squares means, p-values were from MMRM model with treatment and baseline score as fixed effects, and center as random effect. Restricted Maximum Likelihood (REML) with an unstructured variance-covariance matrix is used for estimation in the MMRM analysis.

Table 14.2.2.1.2
 Summary of Change of Partial Mayo Score from Baseline to Week 8
 PP Analysis set

Study Visit	Placebo (N=XX)	BBT-401-1S (N=XX)
Baseline		
n (missing)	XX (XX)	XX (XX)
Mean (SD)	XX.X (XX.XX)	XX.X (XX.XX)
Median	XX.X	XX.X
Min, Max	XX, XX	XX, XX
Week 8		
n (missing)	XX (XX)	XX (XX)
Mean (SD)	XX.X (XX.XX)	XX.X (XX.XX)
Median	XX.X	XX.X
Min, Max	XX, XX	XX, XX
Change from Baseline to Week 8		
n (missing)	XX (XX)	XX (XX)
Mean (SD)	XX.X (XX.XX)	XX.X (XX.XX)
Median	XX.X	XX.X
Min, Max	XX, XX	XX, XX
LS Mean (SE)	XX.X (XX.XX)	XX.X (XX.XX)
P-Value, Active vs Placebo		0.XXX
LS Mean Difference (SE)		XX.X (XX.XX)
95% CI for Differences		(XX.X, XX.X)

Note: Least Squares means, p-values were from MMRM model with treatment and baseline score as fixed effects, and center as random effect. Restricted Maximum Likelihood (REML) with an unstructured variance-covariance matrix is used for estimation in the MMRM analysis.

Table 14.2.2.2.1
 Summary of Change of Histologic Assessment of Endoscopic Biopsy from Baseline to Week 8
 mITT Analysis set

Study Visit	Placebo (N=XX)	BBT-401-1S (N=XX)
Specimen Region of Origin :XXXXXXXX		
Laboratory Test: XXXXXXXXX		
Baseline		
n (missing)	XX (XX)	XX (XX)
Mean (SD)	XX.X (XX.XX)	XX.X (XX.XX)
Median	XX.X	XX.X
Min, Max	XX, XX	XX, XX
Week 8		

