95% CI for Differences		(XX.X, XX.X)

Note: Least Squares means, p-values were from MMRM model with treatment and baseline score as fixed effects, and center as random effect. Restricted Maximum Likelihood (REML) with an unstructured variance-covariance matrix is used for estimation in the MMRM analysis.

Table 14.2.2.3.2
 Summary of Change of Ulcerative Colitis Endoscopic Index of Severity (UCEIS) Score from Baseline to Week 8
 PP Analysis set

Study Visit	Placebo (N=XX)	BBT-401-1S (N=XX)
Baseline		
n (missing)	XX (XX)	XX (XX)
Mean (SD)	XX.X (XX.XX)	XX.X (XX.XX)
Median	XX.X	XX.X
Min, Max	XX, XX	XX, XX
Week 8		
n (missing)	XX (XX)	XX (XX)
Mean (SD)	XX.X (XX.XX)	XX.X (XX.XX)
Median	XX.X	XX.X
Min, Max	XX, XX	XX, XX
Change from Baseline to Week 8		
n (missing)	XX (XX)	XX (XX)
Mean (SD)	XX.X (XX.XX)	XX.X (XX.XX)
Median	XX.X	XX.X
Min, Max	XX, XX	XX, XX
LS Mean (SE)	XX.X (XX.XX)	XX.X (XX.XX)
P-Value, Active vs Placebo		0.XXX
LS Mean Difference (SE)		XX.X (XX.XX)
95% CI for Differences		(XX.X, XX.X)

Note: Least Squares means, p-values were from MMRM model with treatment and baseline score as fixed effects, and center as random effect. Restricted Maximum Likelihood (REML) with an unstructured variance-covariance matrix is used for estimation in the MMRM analysis.

Table 14.2.2.4.1
Summary of Change of Short Inflammatory Bowel Disease Questionnaire (SIBDQ) from Baseline to Week 8
mITT Analysis set

Study Visit	Placebo (N=XX)	BBT-401-1S (N=XX)
SIBDQ Question #: xxxxxx		
Baseline		
n (missing)	XX (XX)	XX (XX)
Mean (SD)	XX.X (XX.XX)	XX.X (XX.XX)
Median	XX.X	XX.X
Min, Max	XX, XX	XX, XX
Week 8		
n (missing)	XX (XX)	XX (XX)
Mean (SD)	XX.X (XX.XX)	XX.X (XX.XX)
Median	XX.X	XX.X
Min, Max	XX, XX	XX, XX
Change from Baseline to Week 8		
n (missing)	XX (XX)	XX (XX)
Mean (SD)	XX.X (XX.XX)	XX.X (XX.XX)
Median	XX.X	XX.X
Min, Max	XX, XX	XX, XX
LS Mean (SE)	XX.X (XX.XX)	XX.X (XX.XX)
P-Value, Active vs Placebo		0.XXX
LS Mean Difference (SE)		XX.X (XX.XX)
95% CI for Differences		(XX.X, XX.X)

Note: Least Squares means, p-values were from MMRM model with treatment and baseline score as fixed effects, and center as random effect. Restricted Maximum Likelihood (REML) with an unstructured variance-covariance matrix is used for estimation in the MMRM analysis.

Programming Note: Start a new page for each question.

Table 14.2.2.4.2
 Summary of Change of Short Inflammatory Bowel Disease Questionnaire (SIBDQ) from Baseline to Week 8
 PP Analysis set

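### The MMRM for Partial Mayo and SIBDQ has no visit terms and no list of visits, so the SAP does not fix what is printed as the Week 8 difference

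*SAP*

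**What the plan says.** SAP 4.7.1 writes the model out: "The MMRM model will include treatment (whether 1st dose, 2nd dose, or 3rd dose vs. Placebo) and the baseline score as fixed effects", with center random, REML and an unstructured covariance matrix. If that does not converge, the fallbacks are "Toeplitz with heterogeneity, autoregressive with heterogeneity, Toeplitz, and autoregressive". SAP 4.7.2 carries the model to the secondary endpoints ("Similar to the primary efficacy analysis, mixed model repeated measures (MMRM) analyses will be performed for various secondary efficacy endpoints"). Its endpoint list includes "Change from Baseline to Week 8 in Partial Mayo Score" and the matching line for SIBDQ. Neither section has a visit term, a treatment-by-visit term or a list of visits.

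The notes under the table shells repeat the same terms: "Least Squares means, p-values were from MMRM model with treatment and baseline score as fixed effects, and center as random effect". The Partial Mayo and SIBDQ shells (14.2.2.1.1, 14.2.2.1.2, 14.2.2.4.1, 14.2.2.4.2) have rows for baseline, Week 8 and the change to Week 8. The LS means, p-value, LS mean difference and CI sit under the change row.

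Protocol 8.3 gives the schedule: "Partial Mayo Score: Baseline, W4, W8, W12, and W16", and the same visits for SIBDQ. Total Mayo, UCEIS and histology are scheduled only at screening and Week 8. SAP 3.3 moves the placebo group to BBT-401-1S after Week 8.

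Two neighboring places also disagree. The SIBDQ shells run the model item by item ("Programming Note: Start a new page for each question"), while Protocol 8.3.4 describes a total: "Scores range between 10 and 70, reflecting poor to good HRQoL". SAP 4.9 plans no formal biomarker analysis, yet shells 14.2.3.1 and 14.2.3.2 carry p-values from this model.

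**The concern.** A repeated-measures model gives a visit-specific contrast only if treatment is allowed to act differently by visit. With the listed terms there is one treatment coefficient. If two visits enter, that coefficient summarizes both. If one visit enters, the model is not a repeated-measures model, and the covariance list has nothing to estimate. The text is therefore out of step with itself on either reading.

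The Protocol (1.2, Statistical Analysis) wants the group difference described at Week 8. Two programmers following the SAP could print different Partial Mayo and SIBDQ differences, p-values and CIs under the same Week 8 label.

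**Working it through.** The plan gives no effect size, SD, correlation or time course for these endpoints, so there is no figure of its own to reproduce. The text settles that the analysis is ambiguous. Every size below rests on assumed values.

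**1. Week 8 rows only.** Each patient contributes one record. The unstructured matrix reduces to a single residual variance, the Toeplitz and autoregressive fallbacks have no role, and the model is an ANCOVA with random center. Its treatment coefficient targets the Week 8 effect (100%).

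**2. Weeks 4 and 8, listed terms.** With a common treatment coefficient and covariance matrix S over the two visits, the generalized least squares weights are S⁻¹1 / (1ᵀS⁻¹1). Let k be the Week 8 SD divided by the Week 4 SD, and ρ the correlation. Then

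- w8 = (1 − ρk) / (1 + k² − 2ρk), and w4 = 1 − w8
- estimate ÷ Week 8 effect = w8 + w4·f, where f is the Week 4 effect ÷ the Week 8 effect

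For example, k = 1.2 and ρ = 0.5 give w8 = (1 − 0.6)/(1 + 1.44 − 1.2) = 0.40/1.24 = 0.323. With f = 0.5 the share is 0.323 + 0.677 × 0.5 = 0.66.

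| k | ρ | w8 | share, f = 0.5 | share, f = 1 | share, f = 1.25 |
|---|---|---|---|---|---|
| 1.0 | any | 0.500 | 75% | 100% | 112% |
| 1.2 | 0.3 | 0.372 | 69% | 100% | 116% |
| 1.2 | 0.5 | 0.323 | 66% | 100% | 117% |
| 1.2 | 0.7 | 0.211 | 61% | 100% | 120% |
| 0.8 | 0.5 | 0.714 | 86% | 100% | 107% |

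**3. Price of targeting Week 8.** With known covariance, the SE of the Week 8 contrast ÷ the SE of the pooled coefficient is √[(1 + k² − 2ρk)/(1 − ρ²)]. At ρ = 0.5:

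- k = 1.0: √(1/0.75) = 1.155
- k = 1.2: √(1.24/0.75) = 1.286

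**4. Simulation.** Assumed: 2,000 replicates, REML, unstructured covariance, 8 centers with SD 0.5, Week 4 SD 2.0, ρ = 0.5, true Week 8 difference −1.50, f = 0.5, complete data. The corrected model adds visit and treatment-by-visit terms.

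| Active vs placebo | k | Pooled mean | Corrected MMRM mean | Week 8 ANCOVA mean | RMSE, pooled vs corrected |
|---|---|---|---|---|---|
| 12 vs 4 | 1.0 | −1.11 | −1.48 | −1.48 | 1.23 vs 1.24 |
| 12 vs 4 | 1.2 | −0.95 | −1.48 | −1.47 | 1.34 vs 1.50 |
| 12 vs 12 | 1.0 | −1.12 | −1.52 | −1.51 | 0.91 vs 0.91 |
| 12 vs 12 | 1.2 | −1.00 | −1.50 | −1.50 | 0.98 vs 1.02 |

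The correction removes the bias but not the total error, because the bias it removes is offset by a wider SE. With known covariance and f = 0.5, it lowers RMSE only if the true Week 8 effect exceeds 2.3 points (12 vs 4) or 1.6 points (12 vs 12) with equal SDs, and 2.6 or 1.8 points with k = 1.2.

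The two corrected analyses are about equally precise. For 12 vs 4 with equal SDs, the SE is 1.24 (MMRM) and 1.23 (ANCOVA). With 15% of Week 8 values missing completely at random it is 1.40 and 1.42.

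**The case against.** The strongest reply is that the documents already point to Week 8 alone. The response is stated as change to Week 8 in the model text, the endpoint list and the table titles, and the Partial Mayo and SIBDQ shells have no Week 4 row. The MMRM name and covariance list were written in 4.7.1 for Total Mayo, which has one scheduled post-baseline value, so they do no work there. Carrying that model over gives one Week 8 row per patient and a sound estimate. This largely stands. A reader might infer that the SAP commits to a two-visit average; it does not, because no passage enters Week 4.

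A second reply is that MMRM by convention implies visit and treatment-by-visit terms. That is weaker: the SAP lists its terms, and the shell notes repeat the list without them. A programmer who adds them departs from the written plan.

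A third reply is that little depends on it. The Protocol plans no formal inference and asks only for descriptive Week 8 differences. The study is not powered, the documents give no decision rule that uses these p-values, and unmodeled Week 8 means by group stand in the same tables. All of that is true and limits the harm. It does not settle which number belongs in the modeled rows.

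**Conclusion.** The point holds as an unresolved specification with a limited consequence. The better-supported reading, Week 8 only, gives a valid estimate under the wrong model name and with a covariance list that has no role. The other reading, a repeated-measures fit to Weeks 4 and 8 with the listed terms, prints a weighted average of two visits as Week 8. If the Week 4 effect is half the Week 8 effect, that average is 75% of the Week 8 effect with equal SDs, and 66% with SD ratio 1.2 and correlation 0.5. If the two effects are equal, it is 100%. The SDs, correlation and time course are assumptions.

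Three stronger inferences are not supported:

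- **Weeks 12 and 16 enter the model.** No passage says so. They should still be excluded in words, because they follow the placebo switch.
- **The primary result is affected.** Total Mayo, UCEIS and histology have one scheduled post-baseline value, so their estimates do not change. Only the model name and covariance list are inapt there.
- **The correction makes the estimate more accurate overall.** It corrects the target. In the settings simulated it did not lower RMSE.

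**What to change.** For Partial Mayo and SIBDQ, choose one of these and write it into SAP 4.7.1, 4.7.2 and the shell notes:

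- **MMRM:** enter Weeks 4 and 8 only; add visit and treatment-by-visit terms, and preferably baseline-by-visit; report the Week 8 contrast.
- **ANCOVA:** state that only Week 8 enters, call the model an ANCOVA with random center, and drop the covariance list.

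In either case, exclude Weeks 12 and 16 explicitly.

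Two separate corrections belong with this:

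- **SIBDQ:** model the 10 to 70 total score. The shells name single questions as the response and show no total.
- **Biomarkers:** reconcile SAP 4.9 with shells 14.2.3.1 and 14.2.3.2, by removing the model rows or by using the corrected model.

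The cost is SAP and shell wording plus programming, with no change to the protocol or the data. The statistical cost is a wider SE than the pooled two-visit fit: about 15% with equal SDs and 29% with SD ratio 1.2, at correlation 0.5 with known covariance. In the simulations it was 6–12% and 20–25%.

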4.8 Safety Analyses

The safety and tolerability of treatment will be assessed by summarizing the following:

- AEs
- Treatment-emergent adverse events (TEAEs)
 - By PT
 - By SOC
 - By maximum severity
 - By considered to be related to investigational product by investigator
- Serious Adverse Events (SAEs)
- AE leading to discontinuation
- Vital signs and weight
- Laboratory measurements

- Electrocardiograms (ECGs)

All safety analyses will be based on the safety analysis set. AE rates will be summarized by treatment group and overall, and will be broken down by severity, seriousness and relation to study drug. Physical examinations, vital signs, ECG and standard laboratory results will be summarized with means, standard deviations, medians and ranges for continuous variables and with counts and percentages for categorical variables. Statistical tests are not planned for safety.

4.8.1 Adverse Events

An AE is defined as any untoward medical occurrence in a subject who is administered a medicinal product and that does not necessarily have a causal relationship to the treatment. All AEs will be included in the data listings. Verbatim terms on case report forms will be mapped to preferred terms and system organ classes (SOC) using the Medical Dictionary for Regulatory Activities (MedDRA) (version 19.1).

A Treatment Emergent Adverse Event (TEAE) is defined as an adverse event that occurs or worsens on or after the first dose of study drug. TEAE summary will be displayed by cohort and treatment. Unless otherwise specified, summaries that are displayed by SOC and preferred terms will be ordered alphabetically by SOC, and within each SOC, preferred terms will also be ordered alphabetically. Summaries of the following types will be presented:

- Subject incidence of TEAEs by MedDRA SOC and preferred term.
- Subject incidence of TEAEs by MedDRA SOC, preferred term, and severity. Severity will be recorded as deemed by investigator. At each level of subject summarization, a subject is classified according to the highest severity if the subject reported one or more events.
- Subject incidence of study drug related TEAEs by MedDRA SOC and preferred term.
- Subject incidence of TEAEs by descending incidence of preferred terms.
- Subject incidence of serious TEAEs by MedDRA SOC and preferred term, if applicable.
- Subject incidence of TEAE leading to early termination by MedDRA SOC and preferred term, if applicable.

For each subject and for each adverse event, the duration of the event will be calculated as:

$$\text{Duration of AE} = \text{AE stop date} - \text{AE start date} + 1$$

The duration of AEs will be displayed in the data listing.

4.8.2 Serious Adverse Events

A serious adverse event (SAE) is any AE or suspected adverse reaction that in the view of either the investigator or Sponsor, results in any of the following outcomes:

- Death
- A life-threatening AE: it is defined as an AE or suspected adverse reaction that in the view of the investigator or Sponsor, its occurrence places the patient or subject at immediate

risk of death. It does not include an AE or suspected adverse reaction that, had it occurred in a more severe form, might have caused death.

- Inpatient hospitalization or prolongation of existing hospitalization.
- A persistent or significant incapacity or substantial disruption of the ability to conduct normal life function.
- A congenital anomaly/birth defect.
- Important medical events that may not result in death, life-threatening, or require hospitalization may be considered serious when, based upon appropriate medical judgment, they may jeopardize the patient or subject and may require medical or surgical intervention to prevent one of outcomes listed in the above definition.

Life threatening:

An adverse event or suspected adverse reaction is considered "life-threatening" if, in the view of either the investigator or sponsor, its occurrence places the patient or subject at immediate risk of death. It does not include an adverse event or suspected adverse reaction that, had it occurred in a more severe form, might have caused death.

Hospitalization:

Any adverse event leading to hospitalization or prolongation of hospitalization will be considered as 'serious', UNLESS at least one of the following exceptions is met:

- the admission results in a hospital stay of less than 24 hours OR
- the admission is pre-planned (i.e., elective or scheduled surgery arranged prior to the start of the study)

However, it should be noted that invasive treatment during any hospitalization may fulfill the criteria of 'medically important' and as such may be reportable as a SAE dependent on clinical judgment.

Disability means a substantial disruption of a person's ability to conduct normal life functions.

Important medical event:

As guidance for determination of important medical events see the 'WHO Adverse Reaction Terminology – Critical Terms List'. These terms either see or might be indicative of a serious disease state. Such reported events warrant special attention because of their possible association with a serious disease state and may lead to more decisive action than reports on other terms.

4.8.3 Clinical Laboratory Evaluation

Abnormal laboratory findings without clinical significance (based on the investigator's judgment) should not be recorded as adverse events; however, laboratory value changes requiring therapy or adjustment in prior therapy are considered as adverse events.

Adverse events will be reviewed continuously throughout the study.

Laboratory results (hematology, serum chemistry and urinalysis) will be presented in data listing. Abnormal values will be flagged as high or low relative to the local lab normal ranges, where applicable. Values that are deemed as abnormal, clinically significant will also be flagged.

Laboratory results will be summarized using descriptive statistics at baseline and post-dose. Changes from baseline will also be summarized. Only non-missing assessments at baseline and post-dose will be analyzed.

Any clinically significant lab abnormalities will be determined by the Principal Investigator and will be reported in the AE table summaries.

4.8.4 Vital Signs

Vital signs will be summarized using descriptive statistics at baseline and at each post-dose time point. Changes from baseline will also be summarized.

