### **9.4 Population for Analyses**

The analyses of the efficacy endpoints will be based on a modified Intent-to-Treat (mITT) population. The mITT population consists of all randomized patients who receive at least 1 dose of study medication. Note that, for the analysis of an individual endpoint, it must have a baseline measurement and at least one post-randomization measurement. Therefore, the patients included in an analysis can vary with endpoints since some patients may have the needed data for inclusion in the mITT analysis for some endpoints but not for others. For the efficacy analyses, patients are

counted in the treatment group to which they were randomized, regardless of the treatment received during the course of the trial.

The analysis of the safety endpoints will be based on a Safety population which will include all randomized patients who received at least 1 dose of study medication. Patients are counted in the treatment group based on the treatment they receive.

PK population consists of all randomized patients who receive at least 1 dose of the study medication and have plasma and tissue concentration data.

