3.2 Determination of Sample Size

As this is an initial dose-escalation study, it is appropriately based on only a limited number of patients in each dose cohort. The size of the study is not based on any statistical power calculations and no formal sample size calculation has been done. Based on the experience from the previous studies and the use of a sequential dose-escalation design for this study, a total of 48 patients (16 patients per dose cohort) is considered appropriate for the study.

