3.3 Treatments

Patients will receive a daily oral dose of BBT 401-1S or placebo for the 16 weeks. While patients who are assigned to Active Group will receive BBT-401-1S for the first 12 weeks and then placebo for the last 4 weeks, patients who are assigned to Placebo Group will receive placebo for the first 8 weeks and then BBT-401-1S for last 8 weeks.

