3.4 Randomization and Blinding

A total of 16 subjects in each of the 3 dosing cohorts will be randomized to either active or placebo group in a 3:1 ratio (12 active and 4 placebo) using the electronic data capture (EDC) system in which the randomization code is integrated.

The randomization code will be generated by an unblinded statistician who is not involved with the study. The Sponsor, investigators, patients, and CRO and other relevant personnel involved with the conduct of the study, with the exception of clinical supply staff and the unblinded statistician, will be blinded to the identity of study medication.

For the 1st or 2nd cohort, if the 12th patient (75%) completes Visit 4 (Week 8), the CRO data management (DM) team confirm all clinical data of the 12 patients have no issue and then obtain the written consent from the Sponsor to breaking the code. Per the request of the CRO DM team, the randomization codes of the 12 patients will be opened via the unblinded statistician and notified to the Sponsor for the analysis to determine the next dose. After confirming all clinical data of remaining 4 patients for the 1st or 2nd cohort, the randomization codes will be subsequently opened to the sponsor through the same procedures stated above.

After the last patient of last cohort completes the SFU, the CRO DM team confirms the whole clinical database has no issue and then requests the database lock to the Sponsor. Per the Sponsor's approval on the database lock, the randomization code of all patients will be opened via the unblinded statistician and notified to the CRO for the statistical analysis.

Breaking of the randomization code without sponsor's permission is expressly forbidden except in the event of a medical emergency where the identity of the study medication must be known in order to properly treat the patient. In the event of a medical emergency, it is requested that the investigator make every effort to contact the study monitor or designee prior to breaking the code.

If the blind is broken due to the medical emergency, the subject must be early terminated; a written explanation must be prepared immediately.

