4.8.5 Electrocardiogram

ECG parameters (numeric) will be summarized using descriptive statistics at baseline and at each post-dose time point. Changes from baseline will also be summarized.

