 - 14.3.1.5 Summary of Treatment-Emergent Serious Adverse Events up to Week 8 by System Organ Class and Preferred Term (Safety Analysis set)
 - 14.3.1.6 Summary of Treatment-Emergent Adverse Events up to Week 8 Leading to Study Discontinuation by System Organ Class and Preferred Term (Safety Analysis set)
 - 14.3.2 Laboratory Testings**
 - 14.3.2.1 Summary of Values and Changes of Hematology Parameters by Visit (Safety Analysis set)
 - 14.3.2.2 Summary of Values and Changes of Chemistry Parameters by Visit (Safety Analysis set)
 - 14.3.3 Vital Signs, ECG Data, Physical Examination**
 - 14.3.3.1 Summary of Vital Sign Parameters by Visit (Safety Analysis set)
 - 14.3.3.2 Summary of Electrocardiogram Parameters by Visit (Safety Analysis set)
 - 14.3.3.3 Summary of Physical Examination by Visit (Safety Analysis set)
- 14.4 Pharmacokinetics**
 - 14.4.1 Plasma Concentration**
 - 14.4.1.1 Plasma BBT-401-1S Concentrations (ng/mL) Following the Administration of BBT-401-1S or Placebo (PK Analysis set)
 - 14.4.2 Tissue Concentration**
 - 14.4.2.1 Tissue BBT-401-1S Concentrations (ng/g) Following the Administration of BBT-401-1S or Placebo (PK Analysis set)

List of Data Listings

ICH Heading	Listing Number	Listing Description
16.2		PATIENT DATA LISTINGS
16.2.1		Discontinued Patients
	16.2.1.1	Patient Disposition
16.2.2		Protocol Deviations
	16.2.2.1	Inclusion/Exclusion Criteria Findings – Deviations
16.2.3		Patients Excluded from the Efficacy Summary
16.2.4		Demographics and Baseline Characteristics
	16.2.4.1	Demographics and Baseline Characteristics
	16.2.4.2	Medical History
	16.2.4.3	Prior and Concomitant Medications
16.2.5		Compliance and/or Drug Administration Data
	16.2.5.1.1	Study Drug Administration and Log
16.2.6		Individual Efficacy Response Data
	16.2.6.1	Total Mayo Score
	16.2.6.2	Partial Mayo Score
	16.2.6.3	Histologic Assessment of Endoscopic Biopsy
	16.2.6.4	Ulcerative Colitis Endoscopic Index of Severity
	16.2.6.5	Short Inflammatory Bowel Disease Questionnaire
	16.2.6.6	Biomarkers
16.2.7		Adverse Events Listings
	16.2.7.1	Adverse Events
	16.2.7.2	Serious Adverse Events
	16.2.7.3	Adverse Events Leading to Permanent Withdrawal of Study Treatment or Discontinuation from the Study
	16.2.7.4	Adverse Events Leading to Death
16.2.8		Individual Lab Measures
	16.2.8.1	Hematology
	16.2.8.2	Chemistry
	16.2.8.3	Vital Signs
	16.2.8.4	Electrocardiogram
	16.2.8.5	Physical Examination
16.2.9		Pharmacokinetics
	16.2.9.1	Individual Plasma Concentration Data

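### By-visit lab, vital-sign, ECG and physical-examination tables keep fixed Placebo and BBT-401-1S columns past the planned treatment switch: the Placebo label is wrong at Week 12 and both labels are inverted at Week 16

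*SAP*

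**What the plan says.** **Treatment.** Under SAP 3.3, "patients who are assigned to Active Group will receive BBT-401-1S for the first 12 weeks and then placebo for the last 4 weeks", while "patients who are assigned to Placebo Group will receive placebo for the first 8 weeks and then BBT-401-1S for last 8 weeks". Both groups are therefore on BBT-401-1S in Weeks 8 to 12, and they hold opposite treatments in Weeks 12 to 16.

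**Timing of the summaries.** For vital signs, SAP 4.8.4 states "Vital signs will be summarized using descriptive statistics at baseline and at each post-dose time point". For ECG, SAP 4.8.5 states "ECG parameters (numeric) will be summarized using descriptive statistics at baseline and at each post-dose time point". SAP 4.8.3 summarizes laboratory results at baseline and post-dose, and Protocol 9.5.3 asks for them at each scheduled evaluation by treatment group. The table list in SAP 6 titles all five tables (hematology, chemistry, vital signs, ECG, physical examination) by visit, for example "Summary of Electrocardiogram Parameters by Visit (Safety Analysis set)". Every adverse-event table in the same list stops at Week 8.

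**Layout.** Each of the five shells has one heading row (Placebo, BBT-401-1S, Overall, each with a single N) and generic rows labelled Visit XX. No shell has a sequence label, a period split or a footnote on the switch.

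**Collection.** Protocol 1.3 and 8.2 schedule all of these assessments at Weeks 4, 8, 12 and 16. Laboratory tests and vital signs are also taken at safety follow-up (SFU); ECG and physical examination are not.

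**Grouping rule.** For the safety population, Protocol 9.4 says "Patients are counted in the treatment group based on the treatment they receive". SAP 4.3.3 defines the safety set but gives no grouping rule, and neither document says how grouping by treatment received applies to a patient who changes treatment as planned.

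**The concern.** A column headed Placebo should hold values from patients taking placebo. After Week 8 these columns do not follow the treatment taken. A laboratory or QTc change that arises on BBT-401-1S in the Placebo Group would be tabulated under Placebo at Weeks 12 and 16. The Week 16 values under BBT-401-1S would come from patients who had been on placebo for four weeks.

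Safety is part of the primary objective. Because every listed adverse-event table stops at Week 8, these five tables are the only listed safety summaries that run beyond it. Anyone using them to judge longer exposure, or the first exposure of the Placebo Group, would attribute values to the wrong treatment.

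**Working it through.** **Inputs**
- Allocation per cohort (SAP 3.4): "randomized to either active or placebo group in a 3:1 ratio (12 active and 4 placebo)".
- Planned total (SAP 3.2): "a total of 48 patients (16 patients per dose cohort) is considered appropriate for the study". Check: 3 × (12 + 4) = 48, that is 3 × 12 = 36 active and 3 × 4 = 12 placebo.
- Active Group: BBT-401-1S in Weeks 0–12, placebo in Weeks 12–16.
- Placebo Group: placebo in Weeks 0–8, BBT-401-1S in Weeks 8–16.
- SFU: 2 weeks (+7 days) after the last dose (Protocol 7.3).

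**Rule.** At each visit, compare the column label with the treatment taken in the interval ending at that visit. Matches = 36 × (1 if the Active Group is on BBT-401-1S, otherwise 0) + 12 × (1 if the Placebo Group is on placebo, otherwise 0). No dropout is assumed.

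| Visit | Patients in BBT-401-1S column take | Patients in Placebo column take | Matches, all cohorts | Matches, per cohort |
|---|---|---|---|---|
| Week 4 | BBT-401-1S | placebo | 36 + 12 = 48/48 | 16/16 |
| Week 8 | BBT-401-1S | placebo | 36 + 12 = 48/48 | 16/16 |
| Week 12 | BBT-401-1S | BBT-401-1S | 36 + 0 = 36/48 (75%) | 12/16 |
| Week 16 | placebo | BBT-401-1S | 0 + 0 = 0/48 | 0/16 |

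**SFU (labs and vital signs only).** The last study dose is at about Week 16, so SFU falls at about Week 18. Time since the last BBT-401-1S dose is 18 − 12 = 6 weeks in the Active Group and 18 − 16 = 2 weeks in the Placebo Group. The +7-day window can add up to one week to each. Nobody is on study drug, so neither label is inverted, but neither describes the patients' status.

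**Visits affected.** Labels fail to match at 2 of 5 scheduled post-baseline visits for labs and vital signs (Weeks 12 and 16, out of Weeks 4, 8, 12, 16 and SFU) and at 2 of 4 for ECG and physical examination.

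**Could the fixed columns follow treatment received?** If patients were placed by current treatment, the Placebo column would hold 12 patients at Week 8, 0 at Week 12 and 36 at Week 16. The BBT-401-1S column would hold 36, 48 and 12. One N per column for all visits cannot represent that, so the shells as drawn hold patients in their randomized group without saying so.

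**The case against.** The best defence is that the columns are simply the randomized groups. The documents name those groups Active Group and Placebo Group, each with a fixed sequence, and Protocol 9.5.3 asks for laboratory results by scheduled time and treatment group, which these tables provide. A reader who knows the sequence can decode each row. The tables are descriptive, and no safety tests are planned. The controlled comparison, the adverse-event tables and the dose-selection unblinding all sit at Week 8, where every label is right. The shells name no weeks, so the run to Weeks 12 and 16 is an inference.

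Most of this is correct, and it limits the point to labelling and presentation. It does not remove it. The headings read Placebo and BBT-401-1S, not the group names, and no footnote explains them. The inference about later visits is sound: nothing limits these tables to Week 8, and the assessments are scheduled at Weeks 12 and 16.

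A reader might infer more than the documents support:
- *That the tables contradict Protocol 9.4.* That section contrasts grouping by treatment received for safety with grouping as randomized for efficacy. It gives no rule by period, so this is an unresolved gap rather than a direct contradiction.
- *That the only within-patient comparison before and after drug is lost.* The Active Group also has a pre-drug baseline and an off-drug interval. Week 8, 12 and 16 values for the Placebo Group would appear as separate rows, and the listings hold each patient's values by visit, with dose and product code in Listing 16.2.10.2.
- *That a reported treatment difference would change sign at Week 16.* The safety shells have no between-group difference row, and nothing in the documents establishes that an effect would reverse within four weeks.
- *That all five tables are mislabelled through SFU.* ECG and physical examination are not done at SFU, and at that visit both groups are off study drug.

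**Conclusion.** The concern holds as a defect in how the later visits are labelled. At Week 12 the Placebo column is wrong (12 of 48 planned patients, 4 of 16 per cohort) and the BBT-401-1S column is still right. At Week 16 both columns are inverted (48 of 48, 16 of 16 per cohort). At SFU the labels are uninformative for labs and vital signs. Weeks 4 and 8 are correctly labelled.

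The counts assume full planned enrolment, no dropout and adherence to the planned switch; actual numbers will be smaller if patients leave early. They also rest on reading the generic visit rows as covering every scheduled visit. No sample size, error rate, analysis set or efficacy estimate changes. The change should still be made, because the shells as written would attribute Week 16 safety values to the wrong treatment in the only listed safety summaries that extend past Week 8.

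**What to change.** In SAP 4.8.3 to 4.8.5 and shells 14.3.2.1 to 14.3.3.3:

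1. Keep the Placebo and BBT-401-1S columns for Weeks 4 and 8 only.
2. Show Weeks 12 and 16, and SFU for labs and vital signs, by sequence: BBT-401-1S to placebo, and placebo to BBT-401-1S. State the treatment taken in the interval before each visit; at SFU, state the approximate time since the last BBT-401-1S dose.
3. Name the visits in the shells, and add one sentence to SAP 4.3.3 saying how grouping by treatment received applies across the planned switch.
4. Optionally, for the numeric parameters, add change from Week 8 at Weeks 12 and 16 for the placebo to BBT-401-1S sequence. This does not apply to the physical-examination table, which shows only counts of findings by clinical significance.

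The cost is wording in the SAP and shells and some reprogramming; no new data are needed and patient care does not change. The tables gain a few columns or rows, and the placebo to BBT-401-1S sequence is small (4 patients per cohort, 12 overall), so its summaries will be imprecise.
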